1.4 Potential Risk and Benefit

1.4.1 Potential Risk

The toxicological profile of PDC-1421 was characterized in single and repeat oral dose studies of up to 13 weeks in rats and repeat oral dose studies of up to 28 days in dogs. Genetic toxicology and safety pharmacology have also been conducted. PDC-1421 was observed to be associated with some adverse effects in serum electrolytes and GI function, but none were clinically significant. Therefore, potential risks of PDC-1421 are fluctuated electrolyte level and gastrointestinal discomfort. We monitored these in the Phase I study and there was no deviation of electrolyte level and no significant gastrointestinal discomfort during monitoring in the clinical trial. However, there were non-clinically significant mild lower diastolic blood pressure and lower heart rate in dog telemetry study and it has been only with the 2500 mg/kg, which is around the NOAEL for dogs. The cardiovascular systems will be monitored in the clinical study.

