3.5.4 Dosing Regimen, packing and labeling

Table 14. Summary of dosing regimen

	Part I	Part II
Visits	Once a week (twice in the first week) for 28 days	Biweekly for 42 days
Study drug bags	21 packs for the following week, total 84 packs	42 packs for the following two weeks, total 126 packs
Dosing regimen	Each pack including (1) or (2): (1) 1 capsule of PDC-1421 (380 mg), TID (2) After passing the checkpoint, 2 capsules of PDC-1421 (380 mg), TID	Each pack including (1), (2) or (3): (1) 2 capsules, TID: 1 capsule of PDC-1421 (380 mg) and 1 capsule of placebo TID (2) 2 capsules, TID: 2 capsules of PDC-1421 (380 mg) and 0 capsule of placebo TID (3) Placebo:

		0 capsule of PDC-1421 (380 mg) and 2 capsules of placebo TID
--	--	--

In part I, six subjects each will take 1 or 2 capsules thrice daily for 28 days, sequentially. Subjects are assessed twice in the first week after drug administration and they will receive the study drug bag for the following 7 days every week. In part II, eligible subjects are randomized into one of three treatment arms in a 1:1:1 ratio (one capsule of PDC-1421 Capsule and placebo thrice daily; two capsules of PDC-1421 Capsule thrice daily; two capsules of placebo thrice daily) for 42 days. After the two weeks of drug administration, subjects will return to the center for assessments then get another study drug bag for the following 14 days. The biweekly clinic visits are three times and one week later after the last dose for follow-up.

Investigational drug (PDC-1421 Capsule or placebo) are provided by BioLite, Inc. and stored in Department of Pharmacy of each clinical site. In part I, the first six subjects will take 21 packs with 21 capsules of PDC-1421 Capsule and another six take 21 packs with 42 capsules of PDC-1421 Capsule in every week of trial. In part II, subjects will be dispensed with study drug per 2 weeks which are packaged in a drug bag. A drug bag will contain 42 packs. Depending on the study arms, each pack may contain 2 PDC-1421 Capsules, 2 placebos or 1 PDC-1421 Capsule plus 1 placebo. Each subject will be administered 126 packs in the end of trial. The drug bag of investigational drug is clearly labeled as following:

For Part I-low dose (380 mg TID):

Test Drug: PDC-1421 Capsule

Amount: capsules (reserved capsules included)

Subject Number:

Drug Pack Number:

Study Protocol: BLI-1005-002

Drug Appearance: Brown capsule containing yellow powder

Major Component: Each capsule contains 380 mg of PDC-1421

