4.1 Inclusion Criteria

1. Outpatients aged 20-65 years.
2. Subjects must be able to understand and willing to sign informed consent.
3. Female subjects of child-bearing potential must test negative to pregnancy and use appropriate birth control method from the beginning of study to the 15 days later after ending of study.
4. Met criteria for MDD without psychotic features as defined by the Diagnostic and Statistical Manual of Mental Disorders, Fourth Edition Text Revision® (DSM-IV-TR) and confirmed by use of the Mini International Neuropsychiatric Interview (MINI).
5. 17-item HAM-D (Hamilton Rating Scale for Depression) total score ≥ 20 and CGI (Clinical Global Impression) total score ≥ 4 .

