4.3 Subject Recruitment and Screening

[figure not shown]
At Visit 1, Investigator will introduce the proposed clinical study to subjects who are interesting in this study. If a subject is willing to undergo an informed consent process based on GCP and participate in our study, the subject will be examined as described in section 5.2. At Visit 2, based on Visit 1 measurements, subject who meets the recruitment criteria will be enrolled in this study.

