4.5 Early Withdrawal of Subjects

Subjects are not obligated to give reasons for discontinuation from this study. Investigator can ask a subject to be withdrawn from study in the best interest of the subject. Subjects withdrawn from the study due to adverse event(s) must be followed until the events are resolved or stabilized. The discontinuation will result from the following reasons:

- Subjects wish to withdraw.
- Subjects can't obey the regulation of the study.
- Investigator consider that withdrawal from study is the best interest of a subject.
- The subject is pregnant during the trial.

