5.2 Treatment Schedule

Potential subjects will be introduced by Investigator of the study design at Screening. If the subject agrees to participate and signs the consent form, the screening process will begin. Suitability of the subject will be evaluated by inclusion/exclusion criteria. In part I, sequentially, six eligible subjects each take 1 or 2 capsules of PDC-1421 Capsule thrice daily and will be assessed twice in the first week (Visit 3 and 4), every week (Visit 5, 6 and 7) for the following treatment and one week later after the last dose for follow-up (Visit 8). In part II, at the beginning of randomization (Visit 2), subjects who met eligibility criteria will be enrolled into this trial and take the study drug in the assigned dose. Subjects will be assessed biweekly (Visit 3, 4 and 5) and a follow-up (Visit 6). Screening, safety and efficacy assessments will be performed as Table 15 and 16.

Table 15. Part I-schedule of assessments

*On ± 2 days.

*V3 (Week 1/2) only can be conducted in Day 3 or Day 4.

	Screening	Treatment Period							Follow-up
		1	2	3	4	5	6	7	
Visit	1								8
*Week	-2 to -1 ~ 0	0	1/2	1	2	3	4		5
Informed consent	•								
Subject information	•								
Medical history	•	•							
DSM-IV-TR	•								
HAM-D-17	•	•		•	•	•	•		•
CGI	•	•		•	•	•	•		•
MADRS	•	•		•	•	•	•		•
DSSS	•	•		•	•	•	•		•
HAM-A	•	•		•	•	•	•		•
C-SSRS	•	•	•	•	•	•	•		•
Concomitant medication	•	•	•	•	•	•	•		•
Physical examination	•	•	•	•	•	•	•		•
Vital sign	•	•	•	•	•	•	•		•
ECG	•	•	•	•	•	•	•		•
Laboratory examination									
Drug screen	•								
Pregnancy test	•								•
Hematology	•	•			•		•		•
Blood chemistry	•	•			•		•		•
Eligibility evaluation	•								
Drug accountability		•	•	•	•	•	•		
AE/SAE evaluation			•	•	•	•	•		•

Table 16. Part II-schedule of assessments

*On ± 2 days.

** If the interval of visit 1 and visit 2 is within 7 days, Hematology and Blood chemistry test of visit 2 can be skipped.

	Screening	Treatment Period					Follow-up
Visit	1	2	3	4	5	6	
*Week	-2 to -1 ~ 0	0	2	4	6	7	
Informed consent	•						
Subject information	•						
Medical history	•	•					
DSM-IV-TR	•						
HAM-D-17	•	•	•	•	•	•	
CGI	•	•	•	•	•	•	
MADRS	•	•	•	•	•	•	
DSSS	•	•	•	•	•	•	
HAM-A	•	•	•	•	•	•	
C-SSRS	•	•	•	•	•	•	
Concomitant medication	•	•	•	•	•	•	
Physical examination	•	•	•	•	•	•	
Vital sign	•	•	•	•	•	•	
ECG	•	•	•	•	•	•	
Laboratory examination							
Drug screen	•						
Pregnancy test	•						•
Hematology	•	• ^{**}	•	•	•	•	
Blood chemistry	•	• ^{**}	•	•	•	•	

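### No scheduled pregnancy test falls between screening and one week after the last dose; add a pre-dose test at Visit 2 and, secondarily, one mid-treatment test

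*Protocol*

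**What the plan says.** Inclusion criterion 3 (Protocol 4.1) has two parts. First, "Female subjects of child-bearing potential must test negative to pregnancy". Second, such subjects must "use appropriate birth control method from the beginning of study to the 15 days later after ending of study". Protocol 4.3 sets the basis for enrolment: "At Visit 2, based on Visit 1 measurements, subject who meets the recruitment criteria will be enrolled in this study". Section 4.5 then gives "The subject is pregnant during the trial" as a reason for discontinuation.

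The schedule is consistent across Tables 15 and 16, sections 5.2.1 to 5.2.3 and the flowcharts in SAP 5.2.3. A pregnancy test appears at screening (Visit 1) and again at follow-up. The item lists for Visit 2 and for every treatment visit contain none. Section 3.5.4 places the Part II follow-up: "The biweekly clinic visits are three times and one week later after the last dose for follow-up". Part I follow-up, Visit 8, is likewise one week after the last dose (5.2.2).

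Other Visit 2 laboratory work is repeated before dosing, with one exception in Part II: "If the interval of visit 1 and visit 2 is within 7 days, Hematology and Blood chemistry test of visit 2 can be skipped". That rule does not mention the pregnancy test.

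On toxicology, section 1.4.1 says "The toxicological profile of PDC-1421 was characterized in single and repeat oral dose studies of up to 13 weeks in rats", with 28-day repeat dosing in dogs. It adds: "Genetic toxicology and safety pharmacology have also been conducted".

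**The concern.** Pregnancy ends participation, but every scheduled dose falls between the only two scheduled tests. A pregnancy missed at Visit 1 because it was too early to detect, or one that begins during the study, will not be found by a planned test until treatment is over. It could be exposed for up to the full 42 days in Part II or 28 days in Part I.

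The entry result may also be stale. Screening lasts up to two weeks, and the 10-day washout that 5.2.1 requires for a prescribed benzodiazepine can lengthen the wait before dosing. In Part II, bloods more than 7 days old are repeated at Visit 2; the pregnancy test is not.

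The stake is maternal and fetal safety. Protocol 1.2.4 and 1.4.1 describe acute, repeated-dose and genetic toxicology and no reproductive or embryo-fetal study, so on these documents the fetal risk is uncharacterised. Type I error, power and the primary analysis are not affected.

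**Working it through.** **Inputs from the documents** (nominal days from Visit 2, ±2-day visit windows ignored)
- Dosing: 42 days in Part II and 28 in Part I, three packs a day (Protocol 3.5.4, Table 14).
- Follow-up: week 7, day 49 (Part II); week 5, day 35 (Part I).
- Lead from Visit 1 to Visit 2: one to two weeks in 5.2.1. The schedule tables extend the window to week 0, so 0 to 14 days.
- Treatment visits that already draw blood include Part II Visit 4 (day 28) and Part I Visit 5 (day 14).
- Subjects on PDC-1421: two Part II arms of 20, plus 12 in Part I, giving 52.

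**Step 1. The plan's own figure.** 42 × 3 = 126 packs and 28 × 3 = 84 packs, as Table 14 states. All of them are taken between the two scheduled tests.

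**Step 2. Present gap = lead + follow-up day**

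| Lead (days) | Part II | Part I |
|---|---|---|
| 14 | 14 + 49 = 63 | 14 + 35 = 49 |
| 7 | 7 + 49 = 56 | 7 + 35 = 42 |
| 0 | 49 | 35 |

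**Step 3. Gap with the added tests, 14-day lead**
- Part II tests at days −14, 0, 28, 49: gaps 14, 28, 21; longest 28. A week-2 test instead of week 4 would leave 49 − 14 = 35.
- Part I tests at days −14, 0, 14, 35: gaps 14, 14, 21; longest 21.
- Longest dosing stretch without a test: Part II from 42 to max(28, 42 − 28) = 28 days; Part I from 28 to max(14, 28 − 14) = 14 days.
- A positive mid-treatment test leaves 42 − 28 = 14 days (Part II) or 28 − 14 = 14 days (Part I) of dosing that can be stopped.

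**Step 4. Expected extra detections.** Assumed, not in the documents: 30% to 60% of subjects are women of child-bearing potential, and contraception fails at 1% to 9% per year. If a test detects conceptions after some constant lag, the added tests newly catch a span equal to the time from Visit 1 to the last added test: 14 + 28 = 42 days in Part II and 14 + 14 = 28 in Part I.
- On PDC-1421: 40 × 42 + 12 × 28 = 2016 subject-days. Low: 0.3 × 2016/365.25 × 0.01 = 0.02. High: 0.6 × 2016/365.25 × 0.09 = 0.30.
- Split of that range: Visit 2 test, 52 × 14 = 728 subject-days, 0.006 to 0.108; mid-treatment test, 40 × 28 + 12 × 14 = 1288 subject-days, 0.011 to 0.190.
- All 72 subjects: 60 × 42 + 12 × 28 = 2856 subject-days, 0.02 to 0.42.

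**Step 5. False positives on the same 72 subjects.** Extra tests: 72 × 2 = 144, times 0.3 to 0.6, about 43 to 86. At an assumed false-positive rate of 0.1% to 1%: 43.2 × 0.001 = 0.04 to 86.4 × 0.01 = 0.86.

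**The case against.** No rule in the protocol is breached. Criterion 3 asks for a negative test and contraception, and both are provided for. Adverse events and physical findings are reviewed at every visit after dosing starts, and nothing in 4.5 confines withdrawal to scheduled tests, so self-report or an unscheduled test can trigger it. Expected extra detections are below one, and false positives may equal or outnumber them. The Investigator's Brochure, the Data and Safety Monitoring Plan and the consent pages were not available and may cover part of this.

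Most of that stands and limits the weight of the point. It does not supply a scheduled test between Visit 1 and the end of dosing, and it does not refresh an eligibility result that may be two weeks old at first dose.

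The two requests also differ in strength. The Visit 2 test confirms eligibility before exposure. The mid-treatment test still leaves up to 28 days of Part II dosing between tests, so it is secondary.

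A reader might infer three stronger things, none of which the documents support:
- *That the protocol contradicts itself, or that a pregnancy cannot be found during dosing.* Only scheduled detection is late; other routes remain open.
- *That no reproductive toxicity study exists, or that fetal harm is known.* The protocol's summary mentions no such study. The summary may be incomplete, and silence is not evidence of harm.
- *That 0.30 is a ceiling.* It is not. With a detection lag near 14 days, the conceptions newly caught at Visit 2 would mostly precede Visit 1. The contraception requirement starts with the study, so the assumed failure rate need not apply to them. In the other direction, some pregnancies would be self-reported first.

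The statement that the next test comes one week after the last dose describes subjects who reach follow-up as scheduled; 4.5 names no pregnancy test at early withdrawal.

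**Conclusion.** The point holds as one of late detection and is worth acting on because the remedy is cheap. At a 14-day lead the nominal gap between scheduled tests is 63 days in Part II and 49 in Part I; with a shorter lead it falls towards 49 and 35. The calendar figures follow directly from the documents.

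The yield figures do not. They rest on assumed shares of women of child-bearing potential, assumed contraceptive failure and false-positive rates, a 14-day lead and full completion, so they are illustrative and not bounds. They show only that detections are probably below one. The argument is potentially serious harm, a fetal risk that these documents leave uncharacterised, and low cost.

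**What to change.** **Main change.** For women of child-bearing potential, add a same-day pregnancy test at Visit 2, with a negative result before the first dose. It applies even when Part II Visit 2 bloods are skipped under the 7-day rule.

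**Secondary change.** Add one test at an existing blood-draw visit: Part II Visit 4 (week 4) and Part I Visit 5 (week 2). Keep the follow-up test.

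Both go into Protocol Tables 15 and 16, sections 5.2.2 and 5.2.3, and the flowcharts in SAP 5.2.3.

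**Addition to 4.5.** A positive test holds dosing until a confirmatory serum test; discontinue if confirmed. This is a small addition to the withdrawal rule, which now contains neither a hold nor a confirmation step.

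**Cost.** About 43 to 86 extra tests at visits already held, same-day results at Visit 2, and occasional false positives. If a hold lasts 1 to 2 days (assumed), a Part II subject misses 3 to 6 of 126 packs, 2.4% to 4.8%, which alone does not breach the 80% compliance rule for the per-protocol set. The larger burden is the amendment: Protocol 10.2 requires submission to the US FDA, MOHW and the IRB, and approval before use. Dose, endpoints and analysis stay as they are. If enrolment has already closed, the change belongs in the protocol for the next phase.

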5 TREATMENT OF SUBJECTS

5.1 Description of Study Drug

PDC-1421 Capsule is a botanical investigational new drug. Each PDC-1421 Capsule contains 380 mg PDC-1421 drug substance extracted from dry root of *P. tenuifolia*. The detailed information of PDC-1421 Capsule is described in section 1.1. Placebo contains 380 mg corn starch and 20 mg excipient (10 mg silicon dioxide and 10 mg magnesium stearate); the appearance of placebo capsule and composition of excipient are the same as PDC-1421 Capsule.

5.2 Treatment Schedule

Potential subjects will be introduced by Investigator of the study design at Screening. If the subject agrees to participate and signs the consent form, the screening process will begin. Suitability of the subject will be evaluated by inclusion/exclusion criteria. In part I, sequentially, six eligible subjects each take 1 or 2 capsules of PDC-1421 Capsule thrice daily and will be assessed twice in the first week (Visit 3 and 4), every week (Visit 5, 6 and 7) for the following treatment and one week later after the last dose for follow-up (Visit 8). In part II, at the beginning of randomization (Visit 2), subjects who met eligibility criteria will be enrolled into this trial and take the study drug in the assigned dose. Subjects will be assessed biweekly (Visit 3, 4 and 5) and a follow-up (Visit 6). Screening, safety and efficacy assessments will be performed as Table 15 and 16.

Table 15. Part I-schedule of assessments

*On ± 2 days.

*V3 (Week 1/2) only can be conducted in Day 3 or Day 4.

	Screening	Treatment Period							Follow-up
		1	2	3	4	5	6	7	
Visit	1								8
*Week	-2 to -1 ~ 0	0	1/2	1	2	3	4		5
Informed consent	•								
Subject information	•								
Medical history	•	•							
DSM-IV-TR	•								
HAM-D-17	•	•		•	•	•	•		•
CGI	•	•		•	•	•	•		•
MADRS	•	•		•	•	•	•		•
DSSS	•	•		•	•	•	•		•
HAM-A	•	•		•	•	•	•		•
C-SSRS	•	•	•	•	•	•	•		•
Concomitant medication	•	•	•	•	•	•	•		•
Physical examination	•	•	•	•	•	•	•		•
Vital sign	•	•	•	•	•	•	•		•
ECG	•	•	•	•	•	•	•		•
Laboratory examination									
Drug screen	•								
Pregnancy test	•								•
Hematology	•	•			•		•		•
Blood chemistry	•	•			•		•		•
Eligibility evaluation	•								
Drug accountability		•	•	•	•	•	•		
AE/SAE evaluation			•	•	•	•	•		•

Table 16. Part II-schedule of assessments

*On ± 2 days.

** If the interval of visit 1 and visit 2 is within 7 days, Hematology and Blood chemistry test of visit 2 can be skipped.

	Screening	Treatment Period					Follow-up
Visit	1	2	3	4	5	6	
*Week	-2 to -1 ~ 0	0	2	4	6	7	
Informed consent	•						
Subject information	•						
Medical history	•	•					
DSM-IV-TR	•						
HAM-D-17	•	•	•	•	•	•	
CGI	•	•	•	•	•	•	
MADRS	•	•	•	•	•	•	
DSSS	•	•	•	•	•	•	
HAM-A	•	•	•	•	•	•	
C-SSRS	•	•	•	•	•	•	
Concomitant medication	•	•	•	•	•	•	
Physical examination	•	•	•	•	•	•	
Vital sign	•	•	•	•	•	•	
ECG	•	•	•	•	•	•	
Laboratory examination							
Drug screen	•						
Pregnancy test	•						•
Hematology	•	• ^{**}	•	•	•	•	
Blood chemistry	•	• ^{**}	•	•	•	•	
Eligibility evaluation	•						
Drug accountability		•	•	•	•		
AE/SAE evaluation			•	•	•	•	

5.2.1 Screening Phase (Visit 1)

The Screening phase will be done within 1-2 weeks period and intended for diagnosing and assessing the patient for possible inclusion in the study and for providing an adequate washout period. The items of physical, rating scales, laboratory examination and drug accountability at screening are outlined below:

- Informed consent
- Subject information, including date of birth, body height and weight
- Medical history, including any clinically significant psychiatric, neurological, gastrointestinal, renal, hepatic, cardiovascular, respiratory, metabolic, endocrine, hematological or other major disorders
- Drug screen, including alcohol, benzodiazepine, amphetamine/MDMA, opiates, cannabinoid, cocaine, phencyclidine, and barbiturate. If a positive result is determined to be caused by prescription of benzodiazepine instead of subject's drug abuse, a 10-day washout period of the prescribed benzodiazepine is required before being treated with investigational products.
- Pregnancy test
- Physical examination: skin, head, neck, eyes, ears, nose, throat, heart, lungs, abdomen (liver, spleen), neurological examination, lymph node and extremities.
- Vital sign: heart rate, blood pressure, body temperature
- ECG
- Hematology: RBC, WBC, platelets, hematocrit, hemoglobin, prothrombin time (PT), partial thromboplastin time (aPTT)
- Blood chemistry: AST, ALT, LDH, total bilirubin, BUN, serum creatinine, free thyroxine (FT4), TSH, sodium, calcium, potassium, HbA1c, LDL, HDL, triglyceride, cholesterol.
- DSM-IV-TR, HAM-D-17, CGI, MADRS, DSSS, HAM-A, C-SSRS and concomitant medication evaluation.

5.2.2. Part I. - Treatment Period (Visit 2~7) and Follow-up (Visit 8)

Laboratory data, other tests and evaluation results shall be obtained at Screening to determine the appropriateness of subject enrolled in this study. Subjects who meet the eligibility criteria will be enrolled and take test drug at this period. First six eligible subjects will take 1 capsule of PDC-1421 Capsule thrice daily in the first week and be assessed twice in the first week after drug administration. They will receive 21 packs of PDC-1421 Capsule for the following week and be evaluated every week till visit 8. After one week of the last dose administration, subjects are assessed for a follow-up. Then, a checkpoint will be conducted. If subjects have no serious adverse event, the trial can continue to next step. If subjects have serious adverse events, there should be a meeting to consider the possibility of continuing the next step of the study or not. Another six subjects will take 2 capsules of PDC-1421 Capsule and all the visits are the same as previous three subjects'. Then, another checkpoint will be conducted as mentioned above. If subjects have no serious adverse events, the schedule can be conducted to the part II. If subjects have serious adverse events, there should be a meeting to consider the possibility of continuing part II of the study or not. The items of safety and efficacy parameters at treatment period are outlined below:

- Physical examination: skin, head, neck, eyes, ears, nose, throat, heart, lungs, abdomen (liver, spleen), neurological examination, lymph node and extremities.
- Vital sign: heart rate, blood pressure, body temperature
- ECG
- Hematology: RBC, WBC, platelets, hematocrit, hemoglobin, prothrombin time (PT), partial thromboplastin time (aPTT)
- Blood chemistry: AST, ALT, LDH, total bilirubin, BUN, serum creatinine, free thyroxine (FT4), TSH, sodium, calcium, potassium, LDL, HDL, triglyceride, cholesterol
- HAM-D-17, CGI, HAM-A, DSSS, MADRS, C-SSRS and concomitant medication evaluation. (At visit 3, subjects will not need to be assessed for above scales except C-SSRS and concomitant medication evaluation.)
- AE/SAE evaluation
- Drug accountability

Follow-up visit will be performed at visit 8 after one week of the last dose administration.

The test items are outlined in the following:

- Physical examination: skin, head, neck, eyes, ears, nose, throat, heart, lungs, abdomen (liver, spleen), neurological examination, lymph node and extremities.
- Vital sign: heart rate, blood pressure, body temperature
- ECG
- Hematology: RBC, WBC, platelets, hematocrit, hemoglobin, prothrombin time (PT), partial thromboplastin time (aPTT)
- Blood chemistry: AST, ALT, LDH, total bilirubin, BUN, serum creatinine, free thyroxine (FT4), TSH, sodium, calcium, potassium, LDL, HDL, triglyceride, cholesterol.
- HAM-D-17, MADRS, DSSS, HAM-A, CGI and C-SSRS and concomitant medication evaluation.
- Pregnancy test
- AE/SAE evaluation

A Data and Safety Monitoring Plan (DSMP) will be provided in this study and approved by IRB. It describes the risk and benefit to subjects, the type of data or events to be captured under the monitoring plan, the frequency of reporting to IRB, etc.

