3 TRIAL DESIGN

3.1 General Design

Table 11. Summary of general design

[figure not shown]
	Part I	Part II
Design	Open label, multiple center, dose escalation	Double-blind, randomized, parallel group, placebo-controlled
MDD patients	12	60
Treatment	(1) 1 capsule TID, 6 MDD patients, 28 days (2) Checkpoints (3) If passing the checkpoint: 2 capsules TID, another 6 MDD patients, 28 days (4) Checkpoints	Randomly assigned on a 1:1:1 basis to one of the three arms: (1) 1 PDC-1421 Capsule plus 1 placebo TID (2) 2 PDC-1421 Capsule TID (3) 2 Placebo TID for 42 days
Assessment interval	First week: twice, 3-4 days interval; Once a week during the following second to fourth week	Biweekly
Efficacy and safety evaluation	
• Safety evaluation• Efficacy evaluation	
• Primary endpoint: efficacy measurement (MADRS)• Secondary endpoints: other efficacy and safety measurements (MADRS, DSSS, HAM-D-17,

		HAM-A, CGI, C-SSRS, ECG, vital sign, physical examination, hematology, blood chemistry and concomitant medication evaluation)
--	--	---

The screening phase is intended for diagnosing and assessing the patient for possible inclusion in the study and for providing an adequate washout period. The following study will be conducted in two parts. The targeted population of this study is 72 subjects who met the intent-to-treat (ITT) basis, in which 12 are assigned to part I, 60 are assigned to part II. Part I is an open-label study, multiple center and dose escalation evaluation in twelve patients. Six subjects each will be evaluated for any safety concerns at 1 or 2 capsules TID dose for 28 days, sequentially. Each of them will be assessed twice in the first week after administration of PDC-1421 Capsules and once a week in the following treatment. Part II is a randomized, double-blind, placebo-controlled, parallel-group study. 60 subjects will be randomly assigned on a 1:1:1 basis to one of the three treatment arms (1 PDC-1421 Capsule plus 1 placebo TID, 2 PDC-1421 Capsule TID, 2 placebo TID) for 6 weeks (42 days) and evaluated the safety and efficacy every two weeks during the treatment period. The performance of PDC-1421 Capsule on MDD subjects will provide us with valuable information for our next phase of the study.

Figure 1. General design of procedure

[figure not shown]
Part I.

* Subjects are assessed once between visit 2 and 4

➡ Checkpoints

Part II.

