7.3 Adverse Events (AEs)

Adverse event is any unfavorable and unintended symptom, syndrome, medical condition or experience that develops or worsens within the study period. In this Phase II trial, any clinically significant abnormal findings, including causing the subject to withdraw from the study, requiring treatment or causing apparent clinical manifestations, or judged relevant by the investigator, are considered to be AEs and will be monitored and recorded. AE may not be causal relationship with study medication or clinical study. Whether related to study medication or not, CRC shall record the information of AEs in CRF. The information of AEs contains characteristic, onset and duration, frequency, the Investigator's opinion of the relationship to the study drug (unrelated, unlikely, possibly, probably, definitely), outcome (recovered, recovered with residual effects, continuing,

death, lost to follow-up) and severity. Common Terminology Criteria for Adverse Events v4.03 (CTCAE Table.17) is a descriptive terminology and the grading (severity) scale is provided for each AE term.

Table 17. Common Terminology Criteria for Adverse Events

Grade	Description
Grade 1	Mild; asymptomatic or mild symptoms; clinical or diagnostic observations only; intervention not indicated.
Grade 2	Moderate; minimal, local or noninvasive intervention indicated; limiting age-appropriate instrumental activities of daily living (ADL)*.
Grade 3	Severe or medically significant but not immediately life-threatening; hospitalization or prolongation of hospitalization indicated; disabling; limiting self-care ADL†.
Grade 4	Life-threatening consequences; urgent intervention indicated.
Grade 5	Death related to AE.‡

*Instrumental ADL refer to preparing meals, shopping for groceries or clothes, using the telephone, managing money, etc.

†Self-care ADL refer to bathing, dressing and undressing, feeding self, using the toilet, taking medications, and not bedridden.

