7.4 Serious Adverse Events (SAE)

SAE is defined as any significantly untoward medical occurrence, including:

- Death
- Life-threatening condition
- Inpatient hospitalization or prolongation of existing hospitalization
- Persistent or significant disability/incapacity
- Congenital anomaly/birth defect
- Required intervention to prevent permanent impairment/damage

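### The only written criterion for passing either Part I checkpoint is the absence of SAEs; important non-serious effects meet it and do not call the meeting on whether to continue

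*Protocol*

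**What the plan says.** Protocol 5.2.2 places a checkpoint after the one-week follow-up of each six-patient cohort, and it is held in every case: "Then, a checkpoint will be conducted". For the step from 1 to 2 capsules TID the rule has two branches. Without an SAE: "If subjects have no serious adverse event, the trial can continue to next step". With one: "If subjects have serious adverse events, there should be a meeting to consider the possibility of continuing the next step of the study". The second checkpoint repeats the pair for entry to the randomised part: "If subjects have no serious adverse events, the schedule can be conducted to the part II".

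Table 11 in section 3.1 names the gate but adds no criterion: "If passing the checkpoint: 2 capsules TID, another 6 MDD patients, 28 days". The SAP repeats the design (5.2) and marks the checkpoints on its diagram, also without a criterion. Section 3.1 says that each cohort is evaluated for any safety concern, which is wider than SAEs.

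**The concern.** Part I is the first repeated human dosing that these documents describe. Phase I gave single doses to healthy volunteers (protocol 1.5). The two checkpoints are the only progression steps defined before randomisation.

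The risks that the protocol names are electrolyte fluctuation and gastrointestinal discomfort, and it says that the cardiovascular system will be monitored (1.4.1). Effects of this kind can be clinically important without being serious in the regulatory sense. On the written rule they neither fail the checkpoint nor call the meeting. A cohort with several severe but non-serious reactions could move to the doubled dose, or on to Part II, without any review that the protocol requires.

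The gate is also narrower than the sponsor's own Phase I account. Section 1.5 reports dose-limiting toxicity cohort by cohort. It counts two placebo glucose values that appear to be the grade 2 findings in 1.3 for which no intervention was needed. No dose-limiting toxicity is defined for Part I.

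**Working it through.** The documents state no operating characteristic for the checkpoints, so there is no figure to reproduce. The check is mainly textual.

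**1. Where is passing defined?**

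| Place | Bearing on the checkpoint |
|---|---|
| Protocol 3.1, Table 11 | Names the gate, no criterion |
| Protocol 5.2.2 | No SAE: may go on. SAE: meeting |
| Protocol 3.6 | Discretionary stop of the trial, not tied to a checkpoint |
| Protocol 5.2.2, Data and Safety Monitoring Plan (DSMP) | Announced; its described contents do not mention escalation |
| SAP 5.2 and 5.2.1 | Checkpoints marked, no criterion |

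Only the second row defines passing.

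**2. Which important effects fall outside the SAE criterion?** Section 7.3 treats as AEs "any clinically significant abnormal findings, including causing the subject to withdraw from the study", as well as findings that need treatment or that the investigator judges relevant. Its grade 3 reads "Severe or medically significant but not immediately life-threatening; hospitalization or prolongation of hospitalization indicated; disabling; limiting self-care ADL". Section 7.4 lists six outcomes, among them "Inpatient hospitalization or prolongation of existing hospitalization" and disability. Grade 3 and SAE therefore overlap on hospitalisation and disability. What remains outside is:
- a grade 3 event that is severe or limits self-care but meets none of the six outcomes;
- a withdrawal for an AE, which section 4.5 foresees;
- a clinically significant ECG, vital-sign or electrolyte change without a serious outcome.

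**3. How does the rule behave?** Let *s* be the per-patient probability of an SAE and *q* the per-patient probability of a related non-serious event of the kinds above. Assume that the two are independent and that six patients are treated.
- Current rule: P(meeting) = 1 − (1 − *s*)^6. The term *q* does not appear.
- With such an event also calling the meeting: P(meeting) = 1 − (1 − *s*)^6 (1 − *q*)^6.

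The documents give neither rate. With *s* = 0.01 assumed, the current rule gives 1 − 0.9415 = 0.059 whatever *q* is.

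| Assumed *q* | Current rule | With added trigger |
|---|---|---|
| 0.05 | 0.059 | 0.31 |
| 0.10 | 0.059 | 0.50 |
| 0.20 | 0.059 | 0.75 |
| 0.30 | 0.059 | 0.89 |
| 0.50 | 0.059 | 0.99 |

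For example, at *q* = 0.10: 1 − 0.9415 × 0.5314 = 0.50. The table shows how the two rules differ. It does not forecast what Part I would find.

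**4. Figures that are context only.**
- Zero SAEs in six patients leaves a one-sided 95% upper limit of 1 − 0.05^(1/6) = 0.393. Zero in 12 leaves 1 − 0.05^(1/12) = 0.221. These limits describe the cohort size and would be the same after the fix.
- Table 15 gives six post-dose visits (3 to 8) with AE evaluation, ECG and vital signs, so 6 × 6 = 36 of each per cohort if all complete. Chemistry at visits 5, 7 and 8 gives 3 × 6 = 18 panels. These counts show what is available for review, not what is lost.

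**5. Counterweights.** The largest Phase I dose, 3,800 mg, was well tolerated. It is 3,800/760 = 5.0 times the top Part I single dose and 3,800/2,280 = 1.67 times its daily total. The rat NOAEL in Table 10 scales to 483.9 × 60 = 29,034 mg/day, and 29,034/2,280 = 12.7. The dog dose with cardiovascular findings scales to 2,500 × (1,666.7/3,000) × 60 = 83,335 mg/day, and 83,335/2,280 = 36.6.

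**The case against.** The strongest reply is that the checkpoint is not the only safeguard, and that 5.2.2 permits progression rather than requiring it. Section 3.1 sets a purpose wider than SAEs for exactly these cohorts. Section 3.6 lets the investigator or sponsor stop the trial, and mentions severe as well as serious experiences. The investigator can withdraw individuals (4.5). A DSMP approved by the IRB may hold further triggers. Section 7.4 introduces its six outcomes as included in the definition rather than as exhausting it, so a severe event that limits self-care might be classed as an SAE.

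Most of this stands as mitigation. It rules out a stronger reading that a reader might infer, namely that non-serious effects could not stop escalation or that the safety data would be ignored. The documents do not say either. Nor do all grade 3 events escape the criterion: some are plainly SAEs, and others are uncertain because the abbreviations section gives the same six outcomes as what looks like a closed list.

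None of it supplies a second progression criterion, however. The permissive wording names nothing else to weigh. Section 3.6 is comparative and discretionary, while Part I is sequential and open-label with no concurrent control. The DSMP is not among these documents.

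A further objection is that a trigger on every clinically significant finding would be too broad, since 7.3 reaches anything needing treatment or judged relevant. That is right, and the fix therefore carries a relatedness condition.

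**Conclusion.** The point holds as a gap in a written safety rule. The protocol and SAP state one criterion for each checkpoint, the absence of SAEs, and one trigger for the meeting, an SAE. Non-serious effects have no weight in that rule: six of six affected patients would still meet it.

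The practical consequence cannot be sized, because the documents give no rate for such events. Phase I and the animal margins give no reason to expect toxicity. A reader might take the 39% limit as the size of the defect, but it reflects six patients and would not change with the rule. The gap does not affect the Part II primary analysis.

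The conclusion assumes that the DSMP, which was not seen, holds no checkpoint triggers. It also assumes that at least some severe events would be classed as non-serious under 7.4.

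Both checkpoints have probably been held. SAP 6.4.2 divides drug and placebo batches by dates in February and March 2018, and placebo is used only in Part II.

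**What to change.** Add to protocol 5.2.2:

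> At each checkpoint the graded AEs, AE withdrawals, ECG, vital signs and electrolytes of the cohort are reviewed. The meeting is also held if any patient had a grade 3 or higher AE, a withdrawal for an AE, or a clinically significant ECG, vital-sign or electrolyte change, where the event is judged at least possibly related to study drug.

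The relatedness scale is already in 7.3. Clinically significant laboratory and vital-sign results and ECG transitions are already to be summarised (SAP 6.5.3, 6.5.5 and 6.5.6), so no new grading is needed. The decision stays with the meeting. If the DSMP already holds such triggers, a cross-reference is enough.

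The cost is two sentences and a short review of six patients' existing data at each checkpoint. No visits, tests or patients are added. With two checkpoints there can be at most two further meetings, each with a possible short delay.

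If the checkpoints are past, the study report should state which of these data each checkpoint reviewed, and whether any such event had occurred by then. The planned tables by part and treatment show the events, but not what was considered at each checkpoint or when.
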